10.0 Regulatory, Ethical, and Study Oversight

10.1 Statement of Compliance

This study will be conducted in accordance with this protocol, FDA and applicable local regulatory requirements.

Before enrollment of participants into this study, the IRB will review and approve the protocol, informed consent documents, any promotional material/advertisements, and any other written information to be provided to the participants. The Package Insert for hydroxychloroquine describing the investigational product will be provided to the IRB for review, see Appendix C. Drug information for vitamin D with calcium is provided in Section 6.3. Also see Appendix D. The IRB's composition or a statement that the IRB's composition meets applicable regulatory criteria will be documented.

If the protocol or any other information given to the participant is amended, the revised documents will be reviewed and approved by the IRB, where applicable. The protocol amendment will only be implemented upon the lead site's receipt of approval and, if required, upon the lead site's notification of applicable regulatory authority(ies) approval except for changes necessary to eliminate an immediate hazard to study participants.

10.2 Informed Consent

Written informed consent will embody the elements of informed consent as required by 21 CFR 50.27 and the IRB and will be in accordance with all applicable laws and regulations. Site investigators will enroll participants according to the study eligibility criteria and in compliance with 21 CFR 50, Protection of Human Participants. The investigator will exercise no selectivity so that no bias is introduced from this source.

The site investigator or qualified study team member must obtain documented consent from each potential participant prior to participating in a clinical study or future biomedical research. If there are changes to the participant's status during the study (e.g., health or age of majority requirements), the investigator or study team member delegated this task must ensure the appropriate consent is in place.

A copy of the consent form should be given to the participant before participation in the study.

The initial ICF, any subsequent revised written ICF and any written information provided to the participant must receive Sanford IRB's approval in advance of use. The participant should be informed in a timely manner if new information becomes available that may be relevant to the participant's willingness to continue participation in the study. The communication of this information will be documented in the participant's study chart. Communication may take place in person, over the telephone or by mail.

Specifics about a study and the study population will be added to the consent form template at the protocol level.

10.3 Study Participant Confidentiality

The investigator will comply with applicable participant privacy regulations/guidance as described as per the Health Insurance Portability and Accountability Act (HIPAA) and any additional local regulations.

The lead site is committed to safeguarding participant confidentiality, to the greatest extent possible. Unless required by law, only the investigator, lead site (or representative), IRB, and/or regulatory authorities will have access to confidential medical records that might identify the participant by name.

The participant must be informed that his/her personal study-related data will be used by the lead site in accordance with local data protection law. The level of disclosure must also be explained to the participant.

The participant must be informed that his/her medical records may be examined by Clinical Research Staff for quality data review at each site or other authorized personnel appointed by the lead site, by appropriate IRB members, and by inspectors from regulatory authorities.

10.4 Risks and Benefits

Potential participants will be informed of the risks and benefits of, as well as alternatives to, trial participation. At a minimum, trial designs will take into account the local standard of care.

All participation in clinical trials is voluntary. Participants enter the trial only after informed consent is obtained. Participants may withdraw from a trial at any time, without any influence on their access to, or receipt of, medical care that may otherwise be available to them.

10.5 Ethics

The study protocol, along with the required informed consent forms, will be approved by the Sanford IRB prior to the initiation of any research procedures (at the site). In addition to details described in the sections above (informed consent, confidentiality, and risks and benefits), the investigators should review and consider ethical ramifications in the design and development of this protocol, in accordance with 21 CFR 50. Protections of Human Participants. The investigators will make every effort to minimize and monitor risks and discomforts to participants throughout the course of the study.

10.6 Study Documentation and Case Report Forms (CRFs)

The data collection tool for this study will be defined CRF/eCRFs to be completed by study-site personnel. The investigator will maintain complete and accurate study documentation in a separate file. Study documentation may include medical records/electronic medical records, records detailing the progress of the study for each participant, signed informed consent forms, drug disposition records, correspondence with the IRB and the study monitor/lead site, screening and consent information, CRFs/eCRFs, AE/SAE reports, laboratory reports, participant diaries/questionnaires, data clarifications requested by the lead site study team, and any other documentation

deemed relevant and pertinent to the study and the study participants. Participant data necessary for analysis and reporting will be entered into a validated database or data system in accordance with Title 21 of the Code of Federal Regulations (21 CFR) Part 11. The site investigator is responsible for the procurement of data and for the quality of data recorded on the CRFs/eCRFs.

10.7 Document and Data Retention

Health information will be used to conduct this study to determine research results. Health information is used to report results of research to federal regulatory agencies, if applicable. Health information from study participants may be included in an audit to ensure that the study follows regulations, policies, and study plans.

All records will be maintained indefinitely. Sanford policy on record retention and destruction specific to research studies will be followed for Sanford sites. Non-Sanford sites will follow their policy for record retention and destruction. Clinical data will be stored indefinitely. If a subject chooses to withdrawal consent to the study, he/she may request to withdraw. No further data will be collected on the subject, but any data collected prior to withdrawal will be and used for analysis.

The site will retain study documentation and data (electronic case report forms) in accordance with applicable regulatory requirements and each site document and data retention policy.

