7.0 Participant Discontinuation/Withdrawal

Participants may withdraw consent at any time for any reason or be withdrawn from the trial at the discretion of the investigator should any untoward effect occur. In addition, a participant may be withdrawn by the investigator if enrollment into the trial is inappropriate, the trial plan is violated, or for administrative and/or other safety reasons.

7.1 Discontinuation of Study Intervention:

A participant must be discontinued from the trial for any of the following reasons:

- The participant withdraws consent.
- Intercurrent illness that prevents further administration of treatment
- The participant has a confirmed positive pregnancy test
- The participant is lost to follow-up

At the discretion of the investigator for safety, behavioral, compliance, or administrative reasons.

For those participants who discontinue study intervention early, each participant will be followed for 30 days for acute adverse event monitoring.

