7.2 Participant Withdrawal from the Study

- A participant may withdraw from the study at any time at his/her own request, or may be withdrawn at any time at the discretion of the investigator for safety, behavioral, compliance, or administrative reasons.
- If the participant withdraws consent for disclosure of future information, any data collected be for that time may be retained.

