7.3 Lost To Follow Up

All reasonable efforts must be made to locate participants to determine and report their ongoing status. This includes follow-up with persons authorized by the participant.

Lost to follow-up is defined by:

- The inability to reach the participant after a minimum of two documented phone calls and
- Lack of response by participant to one certified mail letter.

All attempts should be documented in the participant medical record. Should the participant continue to be unreachable, he/she will be considered lost to follow up. Outcome information that is available via electronic medical records will be documented if available.

If it is determined that the participant has died, the site will use permissible local methods to obtain the date and cause of death.

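### Sections 7.1, 7.2 and 10.7 do not agree on data collection after withdrawal, and participants who leave treatment but still consent have no stated collection of infection status

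*Combined protocol and SAP*

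**What the plan says.** Four sections of the combined protocol and SAP bear on this.

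- **Section 7.1** is headed as discontinuation of the intervention, but its rule is "A participant must be discontinued from the trial for any of the following reasons". The first reason is "The participant withdraws consent"; intercurrent illness, pregnancy, loss to follow-up and investigator discretion come after it. It closes: "For those participants who discontinue study intervention early, each participant will be followed for 30 days for acute adverse event monitoring".
- **Section 7.2** lets participants leave at their own request and adds that they "may be withdrawn at any time at the discretion of the investigator for safety, behavioral, compliance, or administrative reasons". Its only data rule is "If the participant withdraws consent for disclosure of future information, any data collected be for that time may be retained".
- **Section 7.3**, for people who cannot be reached: "Outcome information that is available via electronic medical records will be documented if available".
- **Section 10.7**: "If a subject chooses to withdrawal consent to the study, he/she may request to withdraw". It continues: "No further data will be collected on the subject, but any data collected prior to withdrawal will be and used for analysis".

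Table 1 schedules the Outcomes assessment (whether the participant acquired COVID-19) at Day 14, Day 35 and 12 months. Dosing ends on Day 5. Section 9.3 compares infected proportions with Fisher's exact test, gives no rule for missing infection status, and leaves details to a later SAP.

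**The concern.** Take a participant who withdraws consent on Day 4. Section 7.1 promises 30 days of adverse event follow-up; Section 10.7 forbids any further data. Different sites can reasonably follow different sections.

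The larger gap concerns people who have not withdrawn consent. Someone who stops tablets because of illness, or whom the investigator withdraws, is by the wording of 7.1 out of the trial and followed only for adverse events. No section says that their infection status will still be obtained. Because the first scheduled outcome contact comes nine days after the last planned dose, anyone who leaves during dosing without a known positive test has no scheduled outcome assessment.

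What is at stake is the primary comparison. Stopping may depend on tolerability (Appendix C lists nausea, vomiting and diarrhea for hydroxychloroquine), so missing outcomes could differ by arm. Some of them could have been collected with the participant's agreement.

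**Working it through.** **Step 1: set the sections side by side.**

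| Participant | 7.1 | 7.2 | 7.3 | 10.7 |
|---|---|---|---|---|
| Withdraws consent during dosing | Out of the trial; 30 days of adverse event follow-up | Earlier data may be kept, if consent for future disclosure is withdrawn | Not covered | No further data; earlier data used |
| Wants no more contact, would allow record use | As above | No rule | Not covered | No further data, if this counts as withdrawing consent |
| Stops for illness or is withdrawn by the investigator, still consents | Out of the trial; 30 days of adverse event follow-up if stopping early; infection status not named | Investigator withdrawal allowed; no data rule | Not covered | Not covered |
| Lost to follow-up | Listed as a reason | No rule | Outcome taken from the record if available | Not covered |

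Row 1 is a direct conflict between 7.1 and 10.7. It is confined to people who withdraw consent before dosing ends, because the 7.1 sentence is triggered by stopping the intervention early. Row 2 shows the mismatch between 7.2 and 10.7: one ties its rule to future disclosure, the other to any withdrawal of consent. Row 3 is a gap. Row 4 is coherent.

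**Step 2: reproduce the plan's allowance for loss (Section 9.2).** Inputs: 5% v 10% (Cohort A), 15% v 30% (Cohort B), alpha 0.0492, power 90%, 10% dropout. Sidedness is not stated; two-sided is assumed.

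- Exact power of Fisher's test: 90.02% at 610 per arm (A) and 90.04% at 172 per arm (B). The stated sizes reproduce.
- Inflation: 2 × 610 / 0.9 = 1356 and 2 × 172 / 0.9 = 383, rounded up.
- Allowance: 1356 − 1220 = 136 people in A, or 68 per arm; 383 − 344 = 39 in B, or 19.5 per arm.
- Expected events in A: 610 × 0.10 = 61 and 610 × 0.05 = 30.5. In B: 172 × 0.30 = 51.6 and 172 × 0.15 = 25.8.

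Fisher power by share of randomized participants without an outcome is, in both cohorts, about 93% at no loss, 90% at 10%, 88% at 15% and 86% at 20%. Power is therefore protected up to the planned loss. In Cohort A the people who may be missing outnumber the expected events in each arm, so who is missing matters more than how many.

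**Step 3: illustrate bias in Cohort A.** Let *w* be the share uncollected in an arm, *k* the uncollected participants' risk relative to those who stay, and *r* the stayers' rate. Then (1 − *w*)*r* + *wkr* = true rate, so *r* = true rate / (1 − *w* + *wk*). Assume *w* = 0.15 on hydroxychloroquine and 0.05 on placebo; neither figure is in the documents.

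- *k* = 2: 5% / 1.15 = 4.35%; 10% / 1.05 = 9.52%; RR 0.457.
- *k* = 0.5: 5% / 0.925 = 5.41%; 10% / 0.975 = 10.26%; RR 0.527.
- Equal *w* and equal *k* in both arms: the divisor cancels and RR stays 0.50.

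**Step 4: scale it.** The standard error of log RR at 610 per arm is √(0.95/30.5 + 0.90/61) = 0.214, a 95% interval of about 0.33 to 0.76 around 0.50. The shifts are |ln(0.457/0.50)| = 0.09 and ln(0.527/0.50) = 0.05, both under half a standard error.

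**The case against.** The strongest reply has four parts.

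1. *Stopping collection when consent is withdrawn is proper.* This stands. Section 10.7 is right for someone who refuses all further data use. The difficulty is that it is the only option offered, and that 7.1 contradicts it.
2. *The 7.1 sentence concerns safety, not the primary outcome.* This also stands for the conflict itself, which is about adverse event follow-up. The primary-outcome gap comes from what 7.1 and 7.2 leave unsaid about people who still consent. One could argue that Table 1 continues to apply to someone who merely stops tablets. But 7.1 is the section that addresses such people, and it mentions only adverse events.
3. *The consent form may already separate stopping contact from stopping record use.* This cannot be checked, because consent pages were not available.
4. *The size is assumed.* This is correct. The 15% v 5% split averages 10%, so it assigns the whole dropout allowance to uncollected outcomes, although 7.3 recovers some outcomes for lost participants. Section 6.3.10 lists gastrointestinal effects for the placebo too, so a difference between arms is plausible but not shown.

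A reader might also infer that 7.3 contradicts 10.7, since it allows record capture for the lost but not the withdrawn. The documents do not support this: lost participants have not withdrawn consent, so a different rule is coherent. Section 7.3 is better read as evidence that the sponsor already accepts the medical record as an outcome source.

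**Conclusion.** The point holds and should be corrected by amendment. Sections 7.1 and 10.7 cannot both be followed for a participant who withdraws consent during dosing. Sections 7.2 and 10.7 attach their rules to different acts. Participants who stop tablets or are withdrawn by the investigator while still consenting have no stated collection of infection status.

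The size is unknown, because the documents give no withdrawal rate by arm. Under the assumed 15% v 5% the RR moves from 0.50 to between 0.457 and 0.527, which is modest against sampling error. Equal withdrawal with the same relative risk gives no bias, and loss up to 10% leaves power at about 90%.

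Two stronger inferences are not supported. Outcome data are not thrown away: 10.7 keeps and uses everything gathered before withdrawal, and later data are simply not collected. Nor does an early leaver necessarily contribute no outcome: a positive test known before withdrawal (Section 6.9 has the study team act on one) is retained.

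**What to change.** Reconcile Sections 7.1, 7.2 and 10.7 around three categories, recorded when the participant stops or withdraws:

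- (i) **Stops the intervention, or is withdrawn by the investigator, and still consents:** continue the scheduled Day 14 and Day 35 outcome contacts.
- (ii) **Stops contact but allows record use:** apply the 7.3 record check for COVID-19 outcome and SAEs through Day 35.
- (iii) **Withdraws consent for any further data use:** stop collection; keep and use the data to date.

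Restrict the 10.7 bar on further data to (iii), and exempt (ii) and (iii) from the 30-day follow-up sentence in 7.1. Make the text of 7.1 match its heading, so that stopping the intervention is not the same as leaving the trial.

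The cost is amended wording in three sections, one eCRF field, and a record look-up already prescribed for lost participants. The consent form may need one sentence if it does not already offer the choice. The downside is that record-based outcomes are less complete than those from calls, so category (ii) reduces missing data without removing it.

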10.8 Direct Access to Source Data/Documents

The investigator/study site will cooperate and provide direct access to study documents and data, including source documentation for quality data review by the study team at each site, audits by the lead site or lead site's representatives, review by the IRB, and inspections by applicable regulatory authorities. If contacted by an applicable regulatory authority, the investigator will notify the lead site of contact, cooperate with the authority, provide the lead site with copies of all documents received from the authority, and allow the lead site to comment on any responses.

10.9 Protocol Compliance

Deviations from the approved study protocol will be noted by study staff and will be reported to the IRB by the investigator/treating physician per Sanford IRB policy HRP 024 New Information for reporting protocol deviations/violations.

10.10 Publication Policy

Manuscript submission for publication of the results of this study, or any aspect of work directly related to the study, will be decided by the investigators. Any investigator can submit a publication concept proposal including proposed authorship order to the rest of the investigators for review, which will take place within 30 days after a proposal has been submitted.

Appendix A: Abbreviations

| | |
|-------------------|---|
| AE / SAE | Adverse Event / Serious Adverse Event |
| BCVA | Best Corrected Distance Visual Acuity |
| CTCAE | Common Terminology Criteria for Adverse Events |
| CDC | Center for Disease Control |
| CFR | Code of Federal Regulations |
| CHF | Congestive Heart Failure |
| CNS | Central Nervous System |
| COVID | Coronavirus Disease |
| CRF / eCRF | Case Report Form / Electronic Case Report Form |
| ECG | Electrocardiogram |
| EDC | Electronic Data Capture |
| FDA | Food and Drug Administration |
| GCP | Guidelines for Good Clinical Practices |
| HIPAA | Health Insurance Portability and Accountability Act |
| ICF | Informed Consent Form |
| IRB | Institutional Review Board |
| NCI | National Cancer Institute |
| PI | Principal Investigator |
| PO | By Mouth |
| PPE | Personal Protection Equipment |
| SARS-CoV-2 | Severe acute respiratory syndrome coronavirus 2 |
| SD-OCT | Spectral Domain Ocular Coherence Tomography |
| SoA | Schedule of Activities |
| SOC | Standard of Care |
| SRC | Safety Review Committee |
| VF | Visual Field |

Appendix B: Protocol Amendment History

| DOCUMENT HISTORY | |
|--------------------------|-----------------------|
| Document | Date |
| [Amendment X] | [Day-Mon-Year] |
| [Amendment X] | [Day-Mon-Year] |
| [Amendment X] | [Day-Mon-Year] |
| Original Protocol | [Day-Mon-Year] |

Amendment X

Overall Rationale for the Amendment: (Primary reason for this amendment at the top)

| Section # and Name | Description of Change | Brief Rationale |
|--------------------|-----------------------|-----------------|
| [INSERT] | [INSERT] | [INSERT] |
| [INSERT] | [INSERT] | [INSERT] |
| [INSERT] | [INSERT] | [INSERT] |

[figure not shown]

Following chronic oral administration of hydroxychloroquine, significant levels of three metabolites, desethylhydroxychloroquine (DHCC), desethylchloroquine (DCQ), and bidesethylhydroxychloroquine (BDCQ) have been found in plasma and blood, with DHCC being the major metabolite. The absorption half-life was approximately 3 to 4 hours and the terminal half-life ranged from 40 to 50 days. The long half-life can be attributed to extensive tissue uptake rather than through decreased excretion. Peak plasma levels of hydroxychloroquine were seen in about 3 to 4 hours. Renal clearance in rheumatoid arthritis (RA) patients taking hydroxychloroquine sulfate tablets for at least six months seemed to be similar to that of the single dose studies in volunteers, suggesting that no change occurs with chronic dosing. Range for renal clearance of unchanged drug was approximately 16% to 30% and did not correlate with creatinine clearance; therefore, a dosage adjustment is not required for patients with renal impairment. In RA patients, there was large variability as to the fraction of the dose absorbed (i.e., 30% to 100%), and mean hydroxychloroquine levels were significantly higher in patients with less disease activity. Cellular levels of patients on daily hydroxychloroquine have been shown to be higher in mononuclear cells than polymorphonuclear leucocytes.

Microbiology: Malaria: Mechanism of Action: The precise mechanism by which hydroxychloroquine exhibits activity against *Plasmodium* is not known. Hydroxychloroquine, like chloroquine, is a weak base and may exert its effect by concentrating in the acid vesicles of the parasite and by inhibiting polymerization of heme. It can also inhibit certain enzymes by its interaction with DNA.

Activity in vitro and in Clinical Infections: Hydroxychloroquine is active against the erythrocytic forms of chloroquine sensitive strains of *Plasmodium falciparum*, *Plasmodium malariae*, *Plasmodium ovale*, and *Plasmodium vivax*. Hydroxychloroquine is not active against the gametocytes and exoerythrocytic forms including the hypozoitae

stage (*P. vivax* and *P. ovale*) of the *Plasmodium* parasites.

Drug Resistance: *P. falciparum* strains exhibiting reduced susceptibility to chloroquine also show reduced susceptibility to hydroxychloroquine.

Resistance of *Plasmodium* parasites to chloroquine is widespread (see INDICATIONS AND USAGE: Malaria).

Patients in whom chloroquine or hydroxychloroquine have failed to prevent or cure clinical malaria or parasitemia, or patients who acquired malaria in a geographic area where chloroquine resistance is known to occur should be treated with another form of antimalarial therapy (see INDICATIONS AND USAGE: Malaria and WARNINGS).

Rheumatoid Arthritis and Systemic Lupus Erythematosus: Mechanism of Action: The mechanisms underlying the anti-inflammatory and immunomodulatory effects of hydroxychloroquine sulfate tablets are unknown.

INDICATIONS AND USAGE: Malaria: Hydroxychloroquine sulfate tablets are indicated for the treatment of uncomplicated malaria due to *P. falciparum*, *P. malariae*, *P. ovale*, and *P. vivax*.

Hydroxychloroquine sulfate tablets are indicated for the prophylaxis of malaria in geographic areas where chloroquine resistance is not reported.

Limitations of Use in Malaria:

- Hydroxychloroquine sulfate tablets are not recommended for the treatment of complicated malaria.
- Hydroxychloroquine sulfate tablets are not effective against chloroquine or hydroxychloroquine-resistant strains of *Plasmodium* species (see CLINICAL PHARMACOLOGY: Microbiology). Hydroxychloroquine sulfate tablets are not recommended for the treatment of malaria acquired in geographic areas where chloroquine resistance occurs or when the *Plasmodium* species has not been identified.
- Hydroxychloroquine sulfate tablets are not recommended for malaria prophylaxis in geographic areas where chloroquine resistance occurs.
- Hydroxychloroquine sulfate tablets do not prevent relapses of *P. vivax* or *P. ovale* because it is not active against the hypozoitae forms of these parasites. For radical cure of *P. vivax* and *P. ovale* infections, concomitant therapy with an 8-aminoquinoline compound is necessary (see CLINICAL PHARMACOLOGY: Microbiology).

Prior to prescribing hydroxychloroquine sulfate tablets for the treatment or prophylaxis of malaria, consult the Centers for Disease Control and Prevention (CDC) Malaria website (<http://www.cdc.gov/malaria>).

Lupus Erythematosus: Hydroxychloroquine sulfate tablets are indicated for the treatment of chronic discoid lupus erythematosus and systemic lupus erythematosus in adults.

Rheumatoid Arthritis: Hydroxychloroquine sulfate tablets are indicated for the treatment of acute and chronic rheumatoid arthritis in adults.

CONTRAINDICATIONS: Use of hydroxychloroquine sulfate tablets are contraindicated in patients with known hypersensitivity to 4-aminoquinoline compounds.

WARNINGS: Resistant Strains of Malaria: Hydroxychloroquine sulfate tablets are not effective against chloroquine-resistant strains of *P. falciparum* (see CLINICAL PHARMACOLOGY: Microbiology).

Ocular: Irreversible retinal damage has been observed in some patients who had received hydroxychloroquine sulfate. Significant risk factors for retinal damage include daily doses of hydroxychloroquine sulfate greater than 6.5 mg/kg (5 mg/kg base) of actual body weight, durations of use greater than five years, subnormal glomerular filtration, use of some concomitant drug products such as tamoxifen citrate and concurrent macular disease.

A baseline ocular examination is recommended within the first year of starting hydroxychloroquine sulfate tablets. The baseline exam should include: best corrected distance visual acuity (BCVA), an automated threshold visual field (VF) of the central 10 degrees (with retesting if an abnormality is noted), and spectral domain ocular coherence tomography (SD-OCT).

For individuals with significant risk factors (daily dose of hydroxychloroquine sulfate greater than 5.0 mg/kg base of actual body weight, subnormal glomerular filtration, use of tamoxifen citrate or concurrent macular disease) monitoring should include annual examinations which include BCVA, VF and SD-OCT. For individuals without significant risk factors, annual exams can usually be deferred until five years of treatment.

In individuals of Asian descent, retinal toxicity may first be noticed outside the macula. In patients of Asian descent, it is recommended that visual field testing be performed in the central 24 degrees instead of the central 10 degrees.

It is recommended that hydroxychloroquine be discontinued if ocular toxicity is suspected and the patient should be closely observed given

that retinal changes (and visual disturbances) may progress even after cessation of therapy.

Cardiac Effects, Including Cardiomyopathy and QT Prolongation: Postmarketing cases of life-threatening and fatal cardiomyopathy have been reported with use of hydroxychloroquine sulfate tablets as well as with use of chloroquine. Patients may present with atrioventricular block, pulmonary hypertension, sick sinus syndrome or with cardiac complications. ECG findings may include atrioventricular, right or left bundle branch block. Signs or symptoms of cardiac compromise have appeared during acute and chronic treatment. Clinical monitoring for signs and symptoms of cardiomyopathy is advised, including use of appropriate diagnostic tools such as ECG to monitor patients for cardiomyopathy during hydroxychloroquine sulfate tablets therapy. Chronic toxicity should be considered when conduction disorders (bundle branch block/atrio-ventricular heart block) or biventricular hypertrophy are diagnosed. If cardiotoxicity is suspected, prompt discontinuation of hydroxychloroquine sulfate tablets may prevent life-threatening complications.

Hydroxychloroquine sulfate tablets prolong the QT interval. Ventricular arrhythmias and torsades de pointes have been reported in patients taking hydroxychloroquine sulfate tablets (see OVERDOSAGE). Therefore, hydroxychloroquine sulfate tablets should not be administered with other drugs that have the potential to prolong the QT interval (see DRUG INTERACTIONS).

Worsening of Psoriasis and Porphyrria: Use of hydroxychloroquine sulfate tablets in patients with psoriasis may precipitate a severe attack of psoriasis. When used in patients with porphyria the condition may be exacerbated. The preparation should not be used in these conditions unless in the judgment of the physician the benefit to the patient outweighs the possible hazard.

Proximal Myopathy and Neuropathy: Skeletal muscle myopathy or neuropathy leading to progressive weakness and atrophy of proximal muscle groups, depressed tendon reflexes, and abnormal nerve conduction, have been reported. Muscle and nerve biopsies have been associated with curvilinear bodies and muscle fiber atrophy with vacuolar changes. Assess muscle strength and deep tendon reflexes periodically in patients on long-term therapy with hydroxychloroquine sulfate tablets.

Neuropsychiatric Events, Including Suicidality: Suicidal behavior has been rarely reported in patients treated with hydroxychloroquine sulfate tablets.

Hypoglycemia: Hydroxychloroquine sulfate tablets have been shown to cause severe hypoglycemia including loss of consciousness that could be life-threatening in patients treated with or without antidiabetic medications (see DRUG INTERACTIONS and ADVERSE REACTIONS). Patients treated with hydroxychloroquine sulfate tablets should be warned about the risk of hypoglycemia and the associated clinical signs and symptoms. Patients presenting with clinical symptoms suggestive of hypoglycemia during treatment with hydroxychloroquine sulfate tablets should have their blood glucose checked and treatment reviewed as necessary.

PRECAUTIONS: General: Use with caution in patients with gastrointestinal, neurological, or blood disorders, and in those with a sensitivity to quinoline.

Hepatic/Renal Disease: Antimalarial compounds should be used with caution in patients with hepatic disease or alcoholism or in conjunction with known hepatotoxic drugs. A reduction in dosage may be necessary in patients with hepatic or renal disease, as well as in those taking medicines known to affect these organs.

Hematologic Effects/Laboratory Tests: Antimalarial compounds should be used with caution in patients with hepatic disease or alcoholism or in conjunction with known hepatotoxic drugs. Periodic blood cell counts should be performed if patients are given prolonged therapy. If any severe blood disorder such as aplastic anemia, agranulocytosis, leukopenia, or thrombocytopenia, appears which is not attributable to the disease under treatment, consider discontinuation of hydroxychloroquine sulfate tablets.

Hydroxychloroquine sulfate tablets should be administered with caution in patients having glucose-6-phosphate dehydrogenase (G-6-PD) deficiency.

Dermatologic Effects: Dermatologic reactions to hydroxychloroquine sulfate tablets may occur and, therefore, proper care should be exercised when it is administered to any patient receiving a drug with a significant tendency to produce dermatitis.

Drug Interactions: Digoxin: Concomitant hydroxychloroquine sulfate tablets and digoxin therapy may result in increased serum digoxin levels; serum digoxin levels should be closely monitored in patients receiving combined therapy.

Insulin or Antidiabetic Drugs: As hydroxychloroquine sulfate tablets may enhance the effects of a hypoglycemic treatment, a decrease in doses of insulin or antidiabetic drugs may be required.

Drugs that Prolong QT Interval and Other Arrhythmogenic Drugs: Hydroxychloroquine sulfate tablets prolong the QT interval and should not be administered with other drugs that have the potential to induce cardiac arrhythmias. Also, there may be an increased risk of inducing ventricular arrhythmias if hydroxychloroquine sulfate tablets are used concomitantly with other arrhythmogenic drugs.

Mefloquine and Other Drugs Known to Lower the Convulsive Threshold: Hydroxychloroquine sulfate tablets can lower the convulsive threshold. Co-administration of hydroxychloroquine sulfate tablets with other antimalarials known to lower the convulsion threshold (e.g., mefloquine) may increase the risk of convulsions.

Antiepileptic: The activity of antiepileptic drugs might be impaired if co-administered with hydroxychloroquine sulfate tablets.

Methotrexate: Combined use of methotrexate with hydroxychloroquine sulfate tablets have not been studied and may increase the incidence of adverse effects.

Cyclosporin: An increased plasma cyclosporin level was reported when cyclosporin and hydroxychloroquine sulfate tablets were co-administered.

The following interactions have been observed on treatment with the structurally related substance chloroquine phosphate, and therefore cannot be ruled out for hydroxychloroquine.

Praziquantel: Chloroquine has been reported to reduce the bioavailability of praziquantel.

Antacids and Kaolin: Antacids and kaolin can reduce absorption of chloroquine; an interval of at least 4 hours between intake of these agents and chloroquine should be observed.

Cimetidine: Cimetidine can inhibit the metabolism of chloroquine, increasing its plasma level. Concomitant use of cimetidine should be avoided.

Ampicillin: In a study of healthy volunteers, chloroquine significantly reduced the bioavailability of ampicillin.

Information for Patients: Patients should be informed of the early signs and symptoms of toxicity such as rash or visual changes. Patients must see their physicians promptly in case of the appearance of these or of any unusual effects. Periodic laboratory tests may be recommended in some patients. Patients should be fully informed of the potential risks of the use of hydroxychloroquine sulfate tablets, especially in pregnancy and in children.

Carcinogenesis, Mutagenesis, Impairment of Fertility: Long-term studies in animals have not been conducted to evaluate the carcinogenic potential of hydroxychloroquine sulfate tablets.

The mutagenic potential of hydroxychloroquine was not evaluated. However, chloroquine has been shown to be a catalytic inhibitor of DNA repair enzymes (topoisomerase II) and to produce weak genotoxic effects through this mode of action.

Pregnancy - Teratogenic Effects: Human pregnancies resulting in live births have been reported in the literature and no increase in the rate of birth defects has been demonstrated. Embryonic deaths and malformations of anophthalmia and microphthalmia in the offspring have been reported when pregnant rats received large doses of chloroquine.

Nursing Mothers: Caution should be exercised when administering hydroxychloroquine sulfate tablets to nursing women. It has been demonstrated that hydroxychloroquine administered to nursing women is excreted in human milk and it is known that infants are extremely sensitive to the toxic effects of 4-aminoquinolines.

Pediatric Use: Safety and efficacy have not been established in the chronic use of hydroxychloroquine sulfate tablets for systemic lupus erythematosus and juvenile idiopathic arthritis in children. Children are especially sensitive to the 4-aminoquinoline compounds. Most reported fatalities followed the accidental ingestion of chloroquine, sometimes in small doses (0.75 g or 1 g in one 3-year-old child). Patients should be strongly warned to keep these drugs out of the reach of children (see OVERDOSAGE).

Geriatric Use: Clinical studies of hydroxychloroquine sulfate tablets did not include sufficient numbers of subjects aged 65 and over to determine whether they respond differently from younger subjects. However, this drug is known to be substantially excreted by the kidney, and the risk of toxic reactions to this drug may be greater in patients with impaired renal function. Because elderly patients are more likely to have decreased renal function, care should be taken in dose selection and it may be useful to monitor renal function.

ADVERSE REACTIONS: The following adverse reactions have been identified during post-approval use of hydroxychloroquine sulfate tablets or other 4-aminoquinoline compounds. Because these reactions are reported voluntarily from a population of uncertain size, it is not always possible to reliably estimate their frequency or establish a causal relationship to drug exposure.

Blood and Lymphatic System Disorders: Bone marrow failure, anemia, aplastic anemia, agranulocytosis, leukopenia, and

